One approach to improving food tracking adherence is to reduce the burden of the task by simplifying the prescription. Simplification may involve reducing the frequency (e.g., 5 days a

week versus every day) or reducing the amount of intake to track (e.g., some foods/meals vs all foods/meals). To reduce burden, some studies had participants track diet patterns or servings of food groups (instead of calories) and others had participants track by taking photos of their food¹³. A recent systematic review found that 3 out of 4 studies using such abbreviated food tracking approaches reported an association between food tracking and weight loss¹³, which is evidence that the prescription of tracking everything all the time may not be necessary¹⁵. The only approach to tracking that was not associated with weight loss was where participants took photos of foods¹⁶, which suggests this approach may be too far afield from the traditional tracking method to produce meaningful impacts on weight.

We recently conducted an analysis of 153 participants of a digitally delivered weight loss program and found that the optimum threshold of diet tracking that predicted ≥3%, ≥5%, and ≥10% weight loss at 6 months was tracking on 28.5%, 39.4%, and 67.1% of intervention days, respectively. That participants could track about two-thirds of the time and still lose 10% of their baseline weight is an encouraging sign that perfect food tracking adherence is not necessary to be successful. Because participants can reach the weight loss goal while tracking 40-67% of the time, perhaps tracking prescriptions that match those levels would result in less burden and the same or higher success rate. The purpose of this study is to test this very question.

Provide references as appropriate and, when applicable, previous work in animal and/or human studies:

References are provided at the end of the protocol.

Provide previous UConn protocol number, if applicable:

N/A

For each participant population proposed for this study, what is the total # of participants (or, for record reviews, total # of records) required to answer the study question:

The total number of subjects that will be enrolled into the study is 108. It is estimated that we will screen ~1,500 participants to achieve this recruitment goal. Since the initial contact is via an online link, there will be many incomplete responses driving up the number of screened-out participants.

Justification of Sample Size:

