For qualitative and pilot studies, describe how the proposed sample size is appropriate for achieving the anticipated results. For quantitative studies, provide a power analysis that includes effect size, power, and level of significance with references for how the sample size was determined. Explain the rate of attrition and possible number who fail the screening, with references as appropriate.

Leon et al state "power analyses should not be presented in an application for a pilot study that does not propose inferential results."17 As they and others recommend,17,18 we based the sample size of 108 on necessities for examining feasibility thus identifying modifications required to the trial design or study procedures before conducting the full-scale factorial trial. Having 108 participants allows us to recruit online groups of 36, which our previous work shows is feasible and breeds regular engagement.

Enrollment of Oconn Students and/or Employees:
Will UConn students be enrolled?
\square No \boxtimes Yes -> Is it possible that any of the listed study key research personnel teach, or are supervisors of, any of the students?
\boxtimes No \square Yes -> Provide justification for inclusion of this population, provide name of the member of key personnel, and explain how undue influence and bias will be prevented:
Will UConn employees be enrolled?
\square No \boxtimes Yes -> Is it possible that any of the employees report to one or more study key personnel?
$oxtimes$ No \oornightarrow Yes -> Provide justification for inclusion of this population, and explain how undue influence and bias will be prevented:
UConn students and employees may be enrolled if they meet eligibility requirements and are interested in completing the study. Students or employees that report to, are taught by, or have supervisors on key personnel of this project will be excluded from participation.
Enrollment of Key Personnel, Spouses or Dependents/Relatives: Will study key personnel, spouses of study key personnel, or dependents/relative.

S of any study key personnel be enrolled in the study?

 \boxtimes No \square Yes -> Specify, provide justification for inclusion of this population, and explain how undue influence and bias will be prevented:

Recruitment procedures:

For each participant population, provide full detail:

How will the participants be notified or approached about the research (include copies of all recruitment tools, in any media)?

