- Connecting with large businesses to get our ad and/or flyer e-mailed to their staff and/or students
- Qualtrics recruitment panel: Participants on the Qualtrics panel meeting inclusion criteria will be recruited for this study.
 - On the first page of the survey, they will read a brief introduction about this project and if they complete the survey, they will receive Qualtrics incentives regardless of participation in this trial.
 - If they decide to hear more, they will click forward to the next page, which will be our information sheet.
 - If they would like to participate in the trial after reading that sheet, they will click forward to the next page and start the survey.
 - Participants who provide their email will be contacted by the study team for the telephone screening.

To get a representative sample for this study, it is possible we will have to cap certain groups to allow room for other groups (e.g., stop enrolling white women to allow enrolling more males or people of other ethnic/racial backgrounds). In that event, we will send participants generic wording via email (included in accompanying documents) letting them know that we are looking for people with specific characteristics and can only take a certain number of people who have similar characteristics. If they want a further explanation, we will refer them to email [name] to have a more detailed conversation about this decision. As per the grant, the goal of the participant sample is to recruit 50% female and 50% male and anticipate enrolling 30% minority participants. Given that we will be recruiting online, we will not be bound to the racial and ethnic diversity in the local area. We will conduct online advertising in areas that have higher concentrations of ethnic minorities than the US generally so that we can meet our recruitment targets. Because recruiting a gender- and ethnically diverse sample for weight loss studies that do traditional local recruitment can be challenging, this study gives us an opportunity to hone an online recruitment strategy by evaluating the yields from ads in different geographical regions and cities.

How will participant privacy be respected?

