Study Design. Participation starts with a simple information sheet, online eligibility survey, orientation webinar, e-consent, and then another survey to collect baseline assessment data. Eligible participants will then complete an on-boarding process, which includes MyFitnessPal and scale set up. Participants will then be randomized (stratified by gender) and complete an 8-week intervention, and then two assessments at 9-weeks (weigh-in, survey) and 12-weeks (weigh-in).

Recruitment. We will post online recruitment ads that will contain a link to a simple information sheet and an online survey containing the screening questions. Ads that are done with Build Clinical will lead the participants to a landing page that will give them some more information about the study and then will have the link to bring them to the simple information sheet and survey. See the recruitment section (starting on page 6) for full recruitment details.

Screening. Participants will complete screening procedures online since they may be located anywhere in the country. The screening survey will first have a description of the study and the data we will collect from them at that point (the simple information sheet). At the bottom of the information sheet, they can mark whether they are interested in participating or not

interested. If they mark that they are interested, it will bring them to the screening questions to determine eligibility. The survey logic within REDCap will determine eligibility for participation based on participant responses. BuildClinical also had logic to determine eligibility. If they are ineligible, they will be notified after the survey is submitted. If they are eligible to proceed, they will be contacted by the study team via email to book a time to attend a live informational webinar.

We will not require PCP approval since we assess exclusionary medical conditions during the screening process. If conditions are reported that might put the participant at risk during the intervention, they will be excluded.

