Intervention. All participants will join an 8-week counselor-led (counselors go through the DPP lifestyle coach training) Diabetes Prevention Program (DPP) lifestyle intervention in a private Facebook group. Depending on which group participants are randomized to will determine which Facebook group they join. The DPP content will stay the same across all groups. Participants will also be asked to track their diet and exercise on MyFitnessPal as part of the program. Participants will be randomized into one of three groups that differ regarding dietary tracking. Group One will be called the **Daily Tracking Group** and will be asked to track their diet every day in the program. Group Two will be called the **1 On/1 Off Tracking Group** and will be asked to track every other week which would result in 4 weeks of tracking and 4 weeks off from

tracking. Finally, Group Three is called **2 On/1 Off Tracking Group** and will be asked to track for 2 weeks, then they will get a 1-week break and repeat that pattern until the end of the program.

Facebook groups with twice daily pre-programmed posts as in our previous studies (see 4 sample posts below).27,29,30,31 All Facebook groups will be on the "private" setting which means only group members can see the group and its content. Each week's content is based on the corresponding

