Nutritional Literacy. We will report on the % who are considered likelihood of poor nutrition literacy, possibility of poor nutrition literacy, and likelihood of good nutrition literacy. History of Weight loss attempts, diet tracking and diet tracking apps. Using descriptive statistics, we will summarize those who have a history of weight loss attempts, and use of diet tracking and diet tracking apps.

Amount of tracking. We will report the amount of tracking participants did throughout the intervention as well as one month following the intervention.

Contamination. We will report the percentage of participants that used any outside programs that provided weight loss coaching or another app to help with weight loss/exercise.

Burden. Using descriptive statistics, we will summarize burden scores in both treatment conditions. ANOVAs will be used to compare conditions on burden.

Weight loss. We will calculate weight change from baseline to 8 weeks as well as baseline to 12-weeks. As this pilot trial is not powered to detect differences, average changes will not be compared by treatment condition.

Inclusion/Exclusion Criteria

List ALL inclusion and exclusion criteria. Any proposed exclusion criterion based on gender (women of childbearing potential), age, or race must include rationale for the exclusion.

Inclusion Criteria

- 18-65 years old
- BMI 27-45 kg/m²
- Wi-Fi connectivity at home
- Logs into Facebook at least 5 days per week over the past 2 weeks
- Able to participate in the study in English
- Interested in losing weight
- Lives in US

Age justification: Children under 18 require different programming for weight loss and maintenance given their developmental needs. Weight loss is for elderly adults should be medically supervised, something this study is not offering.

Exclusion Criteria

- Pregnant/lactating or plans to become pregnant during study period
- Reports having bipolar disorder, substance abuse, psychosis, an eating disorder, or severe depression
- Had bariatric surgery or plans to have surgery during the study
- Currently taking medication affecting weight
- Has lost ≥5% of weight in past 3 months
- Is participating or intends to participate in another weight loss program during the study
- Chronic pain that interferes with the ability to exercise
- Type 1 Diabetes
- Type 2 Diabetes
- Unable to make dietary changes or increase physical activity
- Unable to walk ¼ mile unaided without stopping

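### Randomisation is stratified by gender, but the burden ANOVA as stated names only condition; adding gender is an optional, nearly free improvement.

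*Protocol*

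**What the plan says.** The Study Design paragraph makes gender the one named stratification factor: "Participants will then be randomized (stratified by gender) and complete an 8-week intervention". Under Recruitment procedures, "the goal of the participant sample is to recruit 50% female and 50% male".

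The Burden paragraph of Data Analysis promises descriptive summaries and then "ANOVAs will be used to compare conditions on burden". It lists no other factor and no covariate. It is the only outcome in that section with a named between-condition test. The Weight loss paragraph says that average changes will not be compared by condition, because the pilot is not powered for it.

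On size and structure, "The total number of subjects that will be enrolled into the study is 108" and "Having 108 participants allows us to recruit online groups of 36". The Intervention paragraph adds "Participants will be randomized into one of three groups that differ regarding dietary tracking" and "Depending on which group participants are randomized to will determine which Facebook group they join".

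**The concern.** Stratifying by gender makes the arms alike in gender mix, so a difference between men and women in burden no longer adds to the chance variation between arm means. An ANOVA by condition alone still counts that difference as residual error. Its reported standard errors are then larger than the design delivers, its test rejects too rarely under the null, and some power is lost. The estimated arm differences are not biased.

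What is at stake is modest: the precision of one secondary, investigator-derived rating in a pilot. It has some value because the protocol says the findings will inform a fully powered trial, and burden is the mechanism that the break schedules are meant to act on.

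**Working it through.** **Plan's own figure.** The protocol gives no power, significance level, effect size or SD. Its sample size reproduces: 3 × 36 = 108.

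**Inputs from the protocol.** Three arms; 36 per arm; a 50/50 gender goal, hence 18 men and 18 women per arm if the goal is met and stratification balances exactly.

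**Assumptions (not in the protocol).** A gender difference in burden of δ, in units of the within-gender SD; two-sided 5% level; everyone answers the burden item; for power, arm means of 0.6, 0.3 and 0 SD.

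**Standard error.** With an equal split, gender adds δ²/4 to the within-arm variance. It adds nothing to the variance of an arm difference, because the mix is the same in each arm. So

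reported SE / true SE = √(1 + δ²/4):
- δ = 0.2: √1.01 = 1.005
- δ = 0.5: √1.0625 = 1.031
- δ = 0.8: √1.16 = 1.077

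A split other than 50/50 gives p(1 − p)δ² in place of δ²/4, which is smaller.

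**Type I error and power.** By condition alone, F = (SSB/2)/(SSW/105), where SSW is a χ² on 104 df plus a noncentral χ² on 1 df with noncentrality 108δ²/4 (1.08, 6.75 and 17.28 for the three values of δ). With gender in the model, that last component leaves the error term and F has 2 and 104 df, so its level is exactly 5%. The noncentrality of the arm effect is 36 × (0.3² + 0² + 0.3²) = 6.48. Four million draws from these components give:

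| δ (SD) | SE too wide by | Type I error, condition only | Power, condition only | Power, with gender |
|---|---|---|---|---|
| 0 | 0% | 5.0% | 60.6% | 60.6% |
| 0.2 | 0.5% | 4.9% | 60.1% | 60.6% |
| 0.5 | 3.1% | 4.2% | 57.4% | 60.6% |
| 0.8 | 7.7% | 3.1% | 52.7% | 60.6% |

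The first row shows the price of adjusting when gender is irrelevant: one of 105 degrees of freedom and no visible loss of power.

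**Where the independence assumption matters.** The arm decides the Facebook group, and 108/3 = 36 equals the stated group size, so each arm appears to be one group. Let ICC be the share of burden variance that members of a group have in common, and ρ the correlation of gender with burden, so that ρ² = (δ²/4)/(1 + δ²/4). The shared group multiplies the variance of an arm mean by about 1 + 35 × ICC. This cancels the effect of omitting gender at ICC = ρ²/36:
- δ = 0.2: 0.0099/36 = 0.0003
- δ = 0.5: 0.0588/36 = 0.0016
- δ = 0.8: 0.1379/36 = 0.0038

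Simulated type I error at ρ = 0.3 (δ = 2 × 0.3/√0.91 = 0.63), 40,000 runs per setting:

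| ICC (assumed) | Condition only | With gender |
|---|---|---|
| 0 | 0.036 | 0.049 |
| 0.003 | 0.052 | 0.068 |
| 0.01 | 0.093 | 0.117 |
| 0.02 | 0.157 | 0.187 |
| 0.05 | 0.334 | 0.371 |

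**The case against.** **The text does not exclude gender.** An ANOVA can carry a second factor, and covariates are often left to an analysis plan, which may exist unseen. This stands. A reader might infer that the plan rejects adjustment; it does not, it is silent. The point is only that the model as stated names condition alone while the same protocol fixes a stratification factor.

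**Gender may not predict burden.** This also stands. The protocol links gender to recruiting a balanced sample, never to burden. At 0.2 SD the effect is negligible, and at zero there is none.

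**The pilot disclaims power.** True, and nothing here breaks a stated target. The Burden paragraph nevertheless plans an inferential comparison, so the model behind it is worth stating.

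**The direction may be wrong for this design.** This is the strongest objection. From the standard-error argument a reader might infer that the burden test as a whole is conservative. The documents do not support that. With what appears to be one counselor-led group per arm, a within-group correlation of a few thousandths offsets the gender effect, and anything larger makes the standard errors too small. Adding gender then raises type I error further, because it removes an error that was partly cancelling another. Two errors that happen to offset are not a reason to keep one, but the gender term must not be presented as making the test valid. The ICC values are assumptions, as the gender differences are.

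**Conclusion.** The mismatch between the stratified design and the stated model holds, but its consequence is conditional and small. If gender predicts burden and outcomes are independent within arms, omitting gender widens the standard error by 0.5% to 7.7% over 0.2 to 0.8 SD. It costs up to about 8 points of power (60.6% against 52.7%) for the assumed arm means. These figures rest on an 18/18 split in every arm and full response, and on gender differences and arm means that the protocol does not supply.

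No claim follows about the overall level of the test. Confounding of arm with Facebook group is a separate and potentially larger problem, and a gender term neither causes nor repairs it. In a pilot this is an optional improvement, worth making because it is nearly free.

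**What to change.** In the Burden paragraph, state that burden will be compared with a linear model containing condition (three arms) and gender as the stratification factor. Report adjusted differences of each break arm from Daily Tracking with 95% confidence intervals. The same edit should reconcile the paragraph's reference to two conditions, and the two groups mentioned in the Baseline section, with the three arms described elsewhere.

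Add a sentence of limitation: if each arm is one Facebook group, arm and group effects cannot be separated, and the standard errors may be too small whether or not gender is in the model.

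The cost is a few sentences and one of 105 degrees of freedom. Gender is already needed for the stratification, so no new data are required.
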